1. **Unconsented data:** SIHHC (hospital discharge projects) taking part in the study (Sites 1-2, 7-13 using clinically led services; Sites 3-4, 14-20 using non-clinically led services) will be asked to provide identifying and demographic data (forename, surname, aliases, date of birth, sex, current or previous postcodes, nationality, ethnicity, NHS number) for service users during the period November 2013 to a maximum of November 2016. However, note that for some services we will collect data that ends before 2016 as some will have been shut down before this time period and in some we may collect data at an earlier point, providing we receive the appropriate permissions and ethical and CAG approvals.
2. **Consented data from a subset of study fieldwork sites (n=6 sites):** We will collect data on 252 individuals across 4 sites with SIHHC (hospital discharge) schemes (two sites that are clinically led (Sites 1&2), two sites that are non-clinically led (Sites 3&4)) and on 126 individuals across two sites with standard /usual care (Sites 5&6), giving 378 individuals in total (63 per site x 6 sites). The data collection for this part of the work is contained in a baseline, exit and 3-month follow up data questionnaire and will collect information on demographic information, along with dates of contact with SIHHC services, past use of health and social care services, mental health services, smoking, alcohol, and drug taking history, prison and homeless history, employment, user satisfaction with service delivery, and data on quality of life (EQ5D). The voluntary sector hospital discharge projects will be asked to help collect this data on behalf of the research team as part of their routine outcomes monitoring and will be reimbursed for doing so at a rate of £20 per completion. The data flow chart shows how this work will be integrated with WP1 for practical purposes.
3. The data flow chart shows how this work will be integrated with WP1 for practical purposes.

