Where feasible, data on access to resources will be collected up to 12-month from discharge. This will allow capturing changes in yearly estimate before and after participating in SIHHC. To determine the effect of the SIHHC we will compare individual service use and health outcome after joining the study (based on 3-month follow-up) with our estimate of their service use had they not participated (one year prior to the enrolment). The specialist schemes will then be compared to the standard schemes which will be assessed in the same way. Cost of care will be estimated multiplying individual-specific health care resource utilization by unit cost using available tariff.

Sample size for economic evaluation:

Data from our 455 controls from Find & Treat provides a mean EQ5D visual analogue scale score of 65 and standard deviation of 25. An important improvement (or worsening) in the EQ5D visual analogue scale (0 to 100) as result of the provision of specialist services to this group would be 10. Using a power of 80% at the 0.05 level of significance (two sided) and a two sample *t* means test it is estimated that a sample size of 100 is required to detect such a change. Based on our previous work it is assumed that of all eligible service users identified, 80% of these will consent to take part in the study, and therefore 126 individuals will need to be approached to achieve this sample size. Therefore, 63 individuals will be approached at each of sites 1-6 (for a total of 378 individuals).

Sensitivity analysis and economic discounting: Cost and effectiveness estimates to be calculated for one year follow up period after entering the study with simulations to 20 years and costs will be discounted at 3.5% per annum. A sensitivity analysis will be carried out in order to examine uncertainties within the cost effectiveness and utility model to examine the uncertainty within the parameters used.

Additional ethical issues

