APPENDIX ONE: FLOW CHARTS

Box 1: Summary Table of Data to be Collected in Each Study Site

	WP1 In-depth fieldwork Topic Guides 1-6	WP2 Consented EQ5D Baseline +Follow-Up Questionnaires	WP2 Unconsented
Realist Evaluation Case Study Sites			
Site 1 – SIHHC Clinically led	✓	✓	✓
Site 2- SIHHC Clinically led	✓	✓	✓
Site 3 – SIHHC Non-clinical (e.g housing link worker)	✓	✓	✓
Site 4 – SIHHC Non-clinical (e.g. housing link worker)	✓	✓	✓
Site 5 – Usual/Standard Care	✓	✓	✓
Site 6 – Usual Standard Care	✓	✓	✓
Other Research Sites			
Site 7 – SIHHC Clinically led			✓
Site 8 – SIHHC Clinically led			✓
Site 9 – SIHHC Clinically led			✓
Site 10 – SIHHC Clinically led			✓
Site 11 – SIHHC Clinically led			✓
Site 12 – SIHHC Clinically led			✓
Site 13 – SIHHC Clinically led			✓
Site 14 – SIHHC Non-clinical (e.g housing link worker)			✓
Site 15 – SIHHC Non-clinical (e.g housing link worker)			✓
Site 16 – SIHHC Non-clinical (e.g housing link worker)			✓
Site 17 – SIHHC Non-clinical (e.g housing link worker)			✓
Site 18 – SIHHC Non-clinical (e.g housing link worker)			✓
Site 19 – SIHHC Non-clinical (e.g housing link worker)			✓
Site 20 – SIHHC Non-clinical (e.g housing link worker)			✓

Box 2: Arrangements for Data Collection in Fieldwork Sites 1-6*

Scheme Typologies Across Fieldwork Sites 1-6

Sites 1&2: In these sites the hospital has access to a specialist integrated hospital discharge scheme (SIHHC) for homeless people which is ‘clinically-led’

Sites 3&4: In these sites the hospital has access to a specialist integrated discharge scheme (SIHHC) for homeless people which is non-clinical (e.g. provides access to housing advice only)

Sites 5&6: In these sites the hospital does not have access to any specialist schemes for discharging homeless service users (i.e. ‘standard or usual care’)

Stakeholder Recruitment (n=60)

In each of these 6 sites, a minimum of 10 stakeholders (practitioners, managers and clinicians) will be recruited for semi-structured interview as part of Work Package 1 (Realist Evaluation). Prospective participants will be given an invitation letter and project information sheet. Informed consent will be ascertained prior to commencement of the interview.

Service user Recruitment (n=378)

In each of these 6 sites a total of 63 service users will be recruited:

In each site:

10 service users will be allocated to Group A

53 service users will be allocated to Group B

Group A (n=10 service users)

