Inclusion Criteria: Service users will be recruited on a first come first served basis until the following demographic categories are filled:

Young Homeless People (1 male/ 1 female) (Age 18-24)

Men in the middle age range (4 male) (Age 25-49) [Known to have the most complex needs (McDonagh, 2011)]

Women in the middle age range (25-49)(2 Female)

Older Homelessness (50+) (1 male/1 female)

NB: Once these categories are filled, homeless service users will then be allocated to **Group B (n=53 service users)**

Group A

Data is to be collected for both Work Package 1 (Realist Evaluation) and Work Package 2 (Comparative Effectiveness and Economic Evaluation)

Homeless service user is on the hospital ward.

Step 1

Seek the support of hospital/scheme discharge coordinators to recruit 10 service users for Group A (n=60)

Step 2

The hospital/scheme discharge coordinator informs the service user about the study, provides an invite letter and a 'Service user Information Leaflet' (Form A). These will be talked through and permission sought to pass the service user's contact details to the research team.

Step 3

A few days after discharge from hospital, the researcher makes contact with the service user (where permission to contact has been given) to arrange a community visit. This will be made by the University Researcher and Peer Researcher working in pairs.

The researcher provides another copy of the 'Service user information Leaflet' (Form A), answers any questions and if the service user is willing to participate

takes informed consent (either written or verbal)(Form A).

Step 4

A semi-structured interview is carried out (Topic Guide 1 – Time 1)

A baseline questionnaire is completed (WP2/BL)

Step 5

Qualitative interview data is transcribed and stored in pass word protected computer at King's College London

Secure upload of consented (WP2BL) individual data to Farr data safe haven

Step 6

The Peer Researcher maintains telephone contact until Time 2 interview takes place at 3 month follow-up (Topic Guide 1 –Interim Telephone)

Notes are taken and passed to King's College London to be stored on pass word protected computer

Step 7

At 3 month follow-up, a semi-structured interview is carried out (Topic Guide 1 – Time 2)

A follow-up questionnaire is completed (WP2/FU)
(University and Peer researcher working in pairs)

Step 8

Qualitative interview data is transcribed and stored in pass word protected computer at King's College London

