Secure upload of consented (WP2FU) individual data to Farr data safe haven (WP2/FU)

Group B

Data is to be collected for Work Package 2 (Comparative Effectiveness and Economic Evaluation) Only

Homeless service user is on the hospital ward.

Step 1

Seek the support of hospital/scheme discharge coordinators to recruit 53 service users for Group B at each site (n=318)

Step 2

The hospital/scheme discharge coordinator informs the service user about the study, provides an invite letter and a 'Service user Information Leaflet' (Form B). These will be talked through and permission sought to pass the service user's contact details to the research team.

Step 3

A few days after discharge from hospital, the researcher makes contact with the service user to arrange a community visit.

The researcher provides another copy of the 'Service user Information Leaflet' (Form B) answers any questions and if the service user is willing to participate takes informed consent (either written or verbal) (Form B)

Step 4

A baseline questionnaire is completed (WP2/BL)

Step 5

Secure upload of consented (WP2/BL) individual data to Farr data safe haven

Step 6

A follow-up questionnaire is completed on exist from the scheme and at three months follow up (WP2/FU)

Step 7

Secure upload of consented (WP2/FU) individual data to Farr data safe haven (WP2)

Box 3: Arrangements for Data Collection in Fieldwork Sites 7-20*

Scheme Typologies Across Sites 7-20

Sites 7-13: In these sites the hospital has access to a specialist integrated hospital discharge scheme for homeless people which is 'clinically-led'

Sites:14-20 In these sites the hospital has access to a specialist integrated discharge scheme for homeless people which is non-clinical (e.g. provides access to housing advice only)

Comparator Databases:

Find and Treat [comparator database]

Hospital Episode Statistics [comparator database representative sample of lowest quintile of deprivation equal in size to the Find and Treat dataset]

Step 1

CAG Approvals in Place

Step 2

Unique study ID created for each individual record and left on site

Step 3

Secure upload of operational service data (non-consented) to Farr data safe haven

[figure not shown]
Step 4

Transfer of sensitive data (first name, surname, dob, sex, current or previous postcodes, nationality, ethnicity, NHS Number, Hospital of admission, Study ID

Step 5:

Transfer of HES ID and HES data back to Farr data safe haven

Box 4: Detailed Data Flow for WP2:

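### Discharge projects may help collect EQ-5D and satisfaction data at the specialist sites only, so the collector can differ between the groups that the third economic analysis compares

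*Protocol*

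**What the plan says.** Item 2 under Data sets used for WP2 describes a baseline, an exit and a 3-month questionnaire for 378 people at six sites. Its content includes EQ-5D, satisfaction with the service and past service use. On collection it says: "The voluntary sector hospital discharge projects will be asked to help collect this data on behalf of the research team". The projects "will be reimbursed for doing so at a rate of £20 per completion". It then points to the data flow chart for how this fits with WP1.

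That flow chart (Appendix One, Box 2) gives the projects no questionnaire role. Discharge coordinators tell the service user about the study and ask permission to pass on contact details. After that:

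- Group A (10 per site): the community visit is made jointly by a university and a peer researcher, who take consent and complete the baseline questionnaire. The 3-month step is again marked "University and Peer researcher working in pairs".
- Group B (53 per site): "A few days after discharge from hospital, the researcher makes contact with the service user to arrange a community visit", and the researcher takes consent. The baseline step that follows is in the passive voice. So is the later step: "A follow-up questionnaire is completed on exist from the scheme and at three months follow up (WP2/FU".

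Of Sites 5 and 6, Box 2 says: "In these sites the hospital does not have access to any specialist schemes for discharging homeless service users". The Health Economics Analysis section says of the third analysis: "The specialist schemes will then be compared to the standard schemes which will be assessed in the same way".

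**The concern.** If the evaluated service helps to put the questions at Sites 1 to 4 and someone else does so at Sites 5 and 6, the collector and the comparison group coincide. No later adjustment can fully separate them.

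The risk is plainest for satisfaction, where people may be asked to judge a service by that service. EQ-5D is self-reported health, so there the risk is narrower: mode of administration, social desirability, and who completes the form.

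The protocol accepts the principle elsewhere. A footnote under Peer Research says that a peer researcher whom the participant knows personally may need to stay out of the interview, because it could inhibit open answers. The WP2 questionnaires have no such safeguard.

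**Working it through.** **Step 1. Set the two places side by side.**

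| Questionnaire | Item 2, Data sets used for WP2 | Appendix One, Box 2 |
|---|---|---|
| Group A, baseline and 3 months | projects help collect | researcher pair |
| Group B, baseline | projects help collect | researcher visits and takes consent; collector implied, not named |
| Group B, exit and 3 months | projects help collect | no collector and no visit named |
| Sites 5 and 6 | no scheme exists to help | same steps as above; exit has no meaning |

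For Group A the two places differ. For Group B the main defect is that nobody is named. At Sites 5 and 6 the item 2 route cannot operate.

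**Step 2. Count who is exposed.** Specialist sites: 4 × 63 = 252. Standard sites: 2 × 63 = 126. Group A: 6 × 10 = 60. Group B: 6 × 53 = 318, which is 318/378 = 84%. The ceiling for project collection is 252. If Group A follows Appendix One, it is 252 − 4 × 10 = 212. Item 2 addresses voluntary sector projects, so it may not reach every scheme at Sites 1 to 4.

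**Step 3. Reproduce the plan's own figure.** From Sample size for economic evaluation: EQ-5D visual analogue scale (VAS), SD 25, difference 10, two-sided 5%, power 80%. The normal formula gives 99 per group and the exact t-test 99.1, so 100. For 80% consent, 100/0.80 = 125, against 126 stated. The figure reproduces.

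**Step 4. Illustrate what a shift would do.** The documents give no size for a collector effect, so b below is an assumption: the net shift, in VAS points, left in the group difference when there is no true difference. With SE = 25 × √(1/n₁ + 1/n₂), the chance of a false positive is 1 − Φ(1.96 − b/SE) + Φ(−1.96 − b/SE).

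| Assumed b | 100 v 100 (SE 3.54) | 200 v 100 (SE 3.06) |
|---|---|---|
| 0 | 5.0% | 5.0% |
| 1 | 5.9% | 6.2% |
| 2 | 8.7% | 10.0% |
| 3 | 13.6% | 16.5% |
| 5 | 29.3% | 37.2% |

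The second column takes about 80% of 252 and 126. Because b is an average over the group, it shrinks in proportion if only some questionnaires are project-administered.

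**Step 5. Ask whether before/after comparison removes it.** The third analysis starts from each person's change. Suppose project administration adds c points. The bias in change is c at follow-up minus c at baseline. If projects administer both, it is c − c = 0. If a researcher does the baseline and a project the follow-up, it is c − 0 = c. Box 2 makes the second pattern quite possible for Group B, since the researcher is present at baseline and nobody is named later. Satisfaction with a service has no value from before that service, so nothing cancels there.

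**The case against.** Much of the opposing case stands.

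- The text says the projects help, and it reimburses the projects. A reader might infer that individual workers are paid for each form on their own service; the document does not say so.
- A reader might infer that Appendix One has researchers complete every questionnaire at all six sites, so that the two places flatly contradict each other. Box 2 supports that only for Group A. Researcher visits at baseline with project help at Group B follow-up would fit both places.
- A reader might infer that both cost-utility analyses confound collector with specialist versus standard care. The second compares the two service types with each other and with Find and Treat controls, and does not name Sites 5 and 6. The comparison at issue belongs to the third.
- A reader might infer that 3-month follow-up would be selective at the specialist sites only. Nothing says that project staff alone would follow people up, or that follow-up at Sites 5 and 6 would be complete.
- The statement about like assessment may refer to the before/after calculation rather than to the collector. Even so, a common calculation does not give a like-for-like comparison if its inputs are gathered differently by group.
- Using services to reach a population that is hard to follow is a defensible trade-off. Fieldwork has 1.5 full-time equivalents (100% plus 50%) for six sites. Group B needs 318 follow-ups at 3 months and 4 × 53 = 212 at exit, 530 in all, so moving every one to researchers is not a small change.

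What remains is that the plan permits collection by the evaluated service in one group, cannot do so in the other, and does not record which happened.

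**Conclusion.** The point holds in this limited form and should be corrected. The plan leaves open who collects 318 of the 378 sets of questionnaires, and one route that it names exists only at Sites 1 to 4. That is at odds with assessing the standard sites alike. It can bias the satisfaction data and the specialist-versus-standard comparison in the third economic analysis.

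The size and even the presence of bias cannot be derived from the document. At most 252 participants could be affected. The false-positive rates above rest on assumed shifts of 1 to 5 points and on the plan's SD of 25. They show sensitivity and do not predict a bias. The HES-linked primary outcomes and the primary cost-effectiveness model do not use these questionnaires and are unaffected.

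**What to change.** 1. Reconcile item 2 with Appendix One so that the baseline questionnaire is completed at the researcher visit already planned at all six sites.
2. State who collects Group B follow-up. Where project help is kept at exit or 3 months, project staff should not administer the satisfaction and EQ-5D items where this can be avoided, for example by self-completion. Step 5 shows why: once a researcher does the baseline, a project-administered follow-up no longer cancels.
3. Add a field recording who administered each questionnaire and how. Since scheme peer mentors may become peer researchers, the field should show when that person also works for the scheme.
4. Limit the comparison of Sites 1 to 4 with Sites 5 and 6 to baseline and 3 months, because scheme exit has no counterpart at the standard sites.
5. Pre-specify a sensitivity analysis of that comparison without project-administered questionnaires.

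The cost is one data field, a little more analysis, and lower precision in the sensitivity analysis. In the extreme case where every Group B follow-up at Sites 1 to 4 is project-administered, 4 × 10 = 40 specialist participants remain against 126. Before attrition, the 95% half-width for VAS is then 1.96 × 25 × √(1/40 + 1/126) = 8.9 points, against 1.96 × 25 × √(1/252 + 1/126) = 5.3 with everyone. The people left may also differ from those excluded, so this analysis exposes a problem more than it cures one.

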4. **Find and Treat Service Unconsented Data:** In order to compare the outcomes of those individuals accessing SIHHC and standard usual care services to a wider homeless population, we will also use data from Find and Treat NHS clinical service that screens for tuberculosis in homeless hostels in London and people using day centres and the street population accessing soup kitchens and cold weather shelters. To identify hospital admissions during the introduction of SIHHC services (November 2013 to November 2016) we will collect all data from Find and Treat since 2008 as this will allow a period of follow up for this community group to have subsequent hospital admissions.
5. **Personal Demographics Service (PDS):** Where available, NHS number will be collected from the 20 sites. Where it is not available we will use the Personal Demographics Service (PDS) at Health & Social Care Information Centre (HSCIC) to undertake a 'list clean' in order to add an NHS number to as many records as possible.
6. **Linked Hospital Episode Statistics (HES) ONS mortality data:** Once these records have been 'list cleaned' they will then be linked by HSCIC to their linked Hospital Episode Statistics (HES) ONS mortality database to provide data on hospitalisation rates (emergency and planned hospital admissions). In addition to data linked from the 18 SIHHC services and Find and Treat, we will also request a geographically comparable and representative sample of lowest quintile of deprivation population in HES (based upon the index of multiple deprivation) equal in size to the Find and Treat dataset during the hospital admission study period of November 2008 to November 2016 and is therefore likely to be 60,000 records. Unlike the F&T group who are homeless, but not necessarily admitted to hospital, we will collect data on this comparison group to enable us to calculate rates for the primary and secondary outcomes in a group of individuals in the most deprived population that have been admitted to hospital and therefore comparable in terms of history of hospital admission to the homeless individuals at the 20 sites.

Comparative Effectiveness Analysis

Data linkage

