We will provide data from the 20 sites and Find and Treat to the Health & Social Care Information Centre (HSCIC). These records will be list cleaned and then linked by HSCIC to the Hospital Episode Statistics (HES) database to provide data on hospitalisations and A&E attendances and deaths for individuals in the 20 sites and Find and Treat database. In order to be able to identify co-morbidities more accurately we will request data on all previous admissions for these groups for identification of

comorbidities but analyses of admission rates will be confined to the period November 2008 – November 2016.

Study design:

We will construct a virtual cohort that will take first date of admission as the entry point (earliest November 2008) or, for control groups an admission matched by month and year restricted to individuals over the age of 18. Exit from the virtual cohort will be at the end of November 2016 or, if earlier, date of death. We will conduct person-level analyses using Poisson regression to compare overall hospitalisation rates, emergency admission rates, all cause mortality and avoidable mortality rates in:

- 1) Homeless people using the different categories of SIHCC service (clinically led services - sites 1&2, 7-13; non-clinically led services - sites 3&4, 14-20)
- 2) Find and Treat Homeless population and sites 5&6 with standard usual care
- 3) Socially deprived non-homeless population.

We will also conduct analyses at the level of the hospital admission whereby through knowledge of the dates of SIHCC involvement and service user group we will be able to classify hospital admissions in the period November 2008- November 2016) into the following groups:

- 1) Admissions in a socially deprived non homeless population
- 2) Admissions in the general homeless population (Find and Treat data)
- 3) Admissions in homeless service users prior to their first engagement with SIHCC
- 4) Admissions in homeless service users where there is evidence of SIHCC support for that admission
- 5) Admissions in homeless service users that occur following SIHCC support but where there is no record of support for the subsequent admission.

We will use Cox regression survival models and Kaplan Meir plots (accounting for clustering at the level of the hospital and individual) to explore how admissions in these groups compare in terms of the following primary outcomes:

- 1) Time from discharge to next A&E attendance

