- 2) 28 day emergency readmission rates (these are a commonly used indicator within the NHS)
- 3) Time from discharge to next hospital inpatient readmission

Secondary outcomes we will examine include:

- 1) Time from admission to death
- 2) Duration of inpatient admission
- 3) Time from admission to mortality from causes amenable to healthcare
- 4) Time from discharge to admission with ambulatory care sensitive (ACS) conditions
- 5) Time from discharge to next planned admission,
- 6) Overall readmission rates
- 7) Unscheduled readmission rates
- 8) All cause mortality
- 9) International Classification of Diseases 10th Revision chapter-specific mortality
- 10) In-patient costs using Health Resource Group

For those service users with quality of life data we will explore how this changes following involvement of services and how it compares to the measures of quality of life derived from studies within Find and Treat service users and within socially deprived non-homeless groups.

A variety of mortality groupings have been developed to identify causes of death that could be considered avoidable through better medical care depending on age at which they occur. The proposals for the Public Health Outcome Monitoring framework take a similar approach and focus on key areas of avoidable mortality namely: mortality from suicide, communicable diseases, excess

seasonal mortality and, in persons aged less than 75 years, cardiovascular disease, cancer, chronic liver disease and chronic respiratory diseases. All of these are useful indicators within homeless populations.

Sample size:

Our sample size is based upon our estimates of historical data from the two types of SIHHC services (non-clinically led SIHHC services vs. clinically led SIHHC). We estimate that each type will have data from approximately 2,208 individuals for the two-year duration of the study, based on the services seeing on average 92 people per month.

From previous health service evaluation data on homeless groups we expect hospitalisation rates to be 0.7 episodes per person-year for homeless individuals admitted to hospital. An important reduction in readmission rates would be 10%. To undertake a sample size calculation to determine the study size required to detect such a reduction in readmission rates, the following variables were defined:

μ_0 = mean readmission rate in the baseline group = 0.7 episodes per person-year

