μ_1 = mean readmission rate in the SIHHC group = 0.6 episodes per person-year

$v=1.96$ =percentage point of the normal distribution corresponding to a 5% two-sided significance level

$u=0.84$ =one-sided percentage point of the normal distribution corresponding to (100%- type II error [FN / (TP + FN)]) at 80% power

Using the following equation we estimated minimum sample size (per group) required for comparison of two rates (readmissions per person-year):

$$\begin{aligned} & (u+v)^2 * (\mu_1 + \mu_0) / (\mu_1 - \mu_0)^2 \\ & (0.84+1.96)^2 *(0.7 + 0.6) / (0.7 - 0.6)^2 \\ & =1019 \text{ person-years per group} \end{aligned}$$

Adjustment for confounders as far as is possible within the analysis results in a doubling of sample size (additional 10% per confounder; likely 10 confounding variables). Therefore 2038 person-years are required per group. Assuming that the SIHHC clinically led and non-clinically led sites see on average 90 service users each month during the study period (which for the purposes of this calculation we have assumed this to be November 2013-November 2015 as many services may have been shut down before this time period and in some we may collect data at an earlier point) we estimate that this translates to a total 2,160 individuals at each of these two types of service.

Follow up: For the primary analysis, individuals will enter the cohort on date of first hospital admission (earliest November 2008) and will be censored at the end of the study period (November 2016) or death, whichever ever comes first.

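### The person-level cohort starts the clock at first admission (from November 2008) but groups people by service use identified mainly from November 2013, so pre-contact time is immortal for death and misclassified for admission rates

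*Protocol*

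**What the plan says.** All references are to the Protocol, Stage 3b (Work Package Two).

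- **Entry.** Comparative Effectiveness Analysis, Study design: "We will construct a virtual cohort that will take first date of admission as the entry point (earliest November 2008". The Follow up paragraph after the sample size calculation repeats this for what it calls the primary analysis: "individuals will enter the cohort on date of first hospital admission (earliest November 2008".
- **Exit.** Study design: "Exit from the virtual cohort will be at the end of November 2016 or, if earlier, date of death".
- **Exposure.** The first person-level group is "Homeless people using the different categories of SIHCC service", divided into clinically led and non-clinically led sites. The other groups are Find and Treat together with standard-care sites 5 and 6, and a deprived non-homeless sample from Hospital Episode Statistics (HES). Control entry is an admission matched on month and year.
- **When users are identified.** Data sets used for WP2, item 1: the services supply data "for service users during the period November 2013 to a maximum of November 2016", with the proviso that "in some we may collect data at an earlier point" if approvals allow. The Find and Treat item dates the introduction of the services to the same window: "To identify hospital admissions during the introduction of SIHHC services (November 2013 to November 2016".
- **Outcomes.** The Poisson models cover hospitalisation, emergency admission, all-cause mortality and avoidable mortality. A separate admission-level analysis sorts admissions into those before first SIHHC engagement, those with support, and later ones without it. The three primary outcomes are listed under that analysis. Its secondary outcomes include "Time from admission to death" and length of inpatient stay.

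**The concern.** A person enters the SIHHC group only by appearing on a service list, mostly from November 2013, yet the clock may have been running since 2008. Anyone who died in between cannot be on a list, so that interval can contain no deaths. A member of the deprived HES sample, matched on month and year of admission, may die at any time afterwards. The SIHHC mortality rate is thus lowered by construction, whatever the services do.

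For hospitalisation and emergency admissions, events do occur in that interval, but no service had yet acted. Counting them as SIHHC experience pulls the group's rate towards the unexposed rate and dilutes any real effect. Adjusting for age, sex, comorbidity and reason for admission does not correct either fault, because the error lies in how time is allocated.

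The primary economic model is linked to this effectiveness work and draws on morbidity and mortality. The second model considers mortality averted, and costs and effects are simulated to 20 years. A spurious survival gain could carry through to both.

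**Working it through.** **1. The plan's own figures.** With rates 0.7 and 0.6, (0.84 + 1.96)² × (0.7 + 0.6) / (0.7 − 0.6)² = 7.84 × 1.3 / 0.01 = 1,019 person-years per group. Doubled for confounders, this is 2,038. Recruitment of 90 a month for 24 months gives 2,160 people per service type. All three reproduce.

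**2. Set-up.** Time 0 is November 2008 and exit is year 8 (November 2016). Contact is taken as uniform over either November 2013 to 2015 (the window assumed in the sample size calculation) or November 2013 to 2016 (the maximum window). Mean time after contact is then 8 − 6.0 = 2.0 years or 8 − 6.5 = 1.5 years. Deaths after contact are ignored; they would raise the pre-contact share.

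Share = mean pre-contact time / (mean pre-contact time + mean post-contact time).

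**3. Share under assumed first-admission dates.** The Protocol gives no such dates. Where a rate is shown, the first admission is the earlier of an exponential waiting time from November 2008 and the contact admission.

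| First admission | Contact 2013–15 | Contact 2013–16 |
|---|---|---|
| All in November 2008 | 6.0/8 = 75% | 6.5/8 = 81% |
| At 0.7 per year (the Protocol's rate) | 4.60/6.60 = 70% | 5.09/6.59 = 77% |
| Uniform from November 2008 to contact | 3.0/5.0 = 60% | 3.25/4.75 = 68% |
| At 0.2 per year | 2.52/4.52 = 56% | 2.88/4.38 = 66% |
| At 0.1 per year | 1.50/3.50 = 43% | 1.74/3.24 = 54% |

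The share passes one half when the mean lag from first admission to contact exceeds the mean post-contact time, about 2.0 or 1.5 years. It is zero for anyone whose first admission is the supported one.

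**4. Mortality with no true effect.** With a constant hazard, deaths arise only after contact but are divided by all person-time. Against controls with no survival requirement, the crude rate ratio is 1 − share: about 0.30 at 70% and 0.23 at 77%. Over the whole table it runs from 0.57 (43%) to 0.19 (81%).

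**5. Admission rates.** If the pre-contact rate is 0.7 and the post-contact rate 0.6, the SIHHC group shows 0.70 × 0.7 + 0.30 × 0.6 = 0.67. The planned ratio 0.6/0.7 = 0.857 becomes about 0.957.

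**6. Person-years if the clock starts at contact.** 2,160 × 2.0 = 4,320, or 2,160 × 1.5 = 3,240, before deaths. Both exceed 2,038. As written, at 0.7 per year, follow-up totals about 14,250 person-years per service type, of which about 9,900 to 11,000 precede any contact.

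**The case against.** **The admission-level analysis already separates time before engagement.** This stands. It uses the dates of SIHHC involvement, all three primary outcomes are listed under it, and they run from discharge. A reader might infer that the primary outcomes share the fault; the Study design text does not support that. The Follow up paragraph does attach the 2008 entry to the primary analysis, so the wording needs clearing up. What remains at admission level is narrower. Where support begins on the ward, a supported patient must still be alive and an inpatient when the team arrives, which affects the two secondary outcomes timed from admission. That effect is probably smaller, and the Protocol gives nothing to size it.

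**The share is assumed.** This stands. A reader might infer that most SIHHC person-time is pre-contact. That follows at the Protocol's 0.7 per year, but that rate is for homeless people admitted to hospital, and carrying it back to 2008 is an assumption. The share can fall below half, and earlier records from some sites would lower it further.

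**Not every comparator is free of the problem.** This stands. Find and Treat members are identified at screening. Consented patients at sites 5 and 6 are approached on the ward and consent after discharge. If their matched admission came earlier, they carry immortal time too. A reader might infer that mortality must favour SIHHC in every comparison. The documents support that mechanism most clearly against the deprived HES sample, and even there case mix affects the observed ratio. Between the two service types the mortality bias partly cancels, though rate differences are still diluted.

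**Could first admission mean first supported admission?** The text does not say so, and admission rates are analysed from November 2008. If that was meant, the wording still has to change.

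**Conclusion.** The concern holds for the person-level Poisson analysis. The entry rule is stated twice, groups are fixed by service use identified mainly five years after the earliest entry date, and nothing divides person-time at contact. Pre-contact time is immortal for the two mortality outcomes and misclassified as exposed for the two admission outcomes.

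The size is conditional: a share of about 43% to 81% under the first-admission patterns tried, and 70% to 77% at the Protocol's own rate. The mortality ratio of 0.30 rests on a 70% share, a constant hazard, no true effect and controls with no survival requirement. The 0.67 v 0.70 result rests on the same share and a pre-contact rate of 0.7. These figures indicate how large the bias could be and do not predict the result. The listed primary outcomes are not affected in this way.

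**What to change.** In Study design and in the Follow up paragraph:

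1. Start person-level follow-up for SIHHC users at discharge from the first SIHHC-supported admission. Start each comparator at discharge from an admission matched to that month and year. For Find and Treat and sites 5 and 6, start no earlier than the date the person was identified.
2. Alternatively, keep the 2008 entry and treat SIHHC contact as a time-varying exposure, with pre-contact time and events counted as unexposed. State that this time comes only from people who survived to contact. It holds no deaths by construction, so it cannot serve as the unexposed reference for mortality.
3. In the admission-level analysis, time death from discharge alive. For length of stay, treat SIHHC contact as time-dependent.
4. Say which analysis the Follow up paragraph means by primary.

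**Cost.** Person-years fall to about 3,240 to 4,320 per service type before deaths, still above 2,038. Each user needs a usable SIHHC contact or supported-admission date. Study design presumes such dates are known, but the unconsented data item lists only identifying and demographic fields, and Appendix One, Box 5 expects few sites to hold every variable. Completeness should be checked site by site, with a rule for users who have no date.
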